#### 2.2 Medication Assisted Treatment

Opioid use disorder, or opioid addiction, is a chronic relapsing disease defined as the loss or reduced control of the use of substance and is expressed through persistence of this use despite the accumulation of negative consequences in health, social, financial, and family life (Auriacombe, Serre et al. 2018). Opioid addiction is most effectively treated as a chronic disease which cannot be cured and requires long-term management strategies (McLellan, Lewis et al. 2000, American Society of Addiction Medicine 2014).

It is well-established that medication-assisted treatment for opioid use disorder, either with methadone, buprenorphine/naloxone, or, naltrexone is safe and effective in reducing and suppressing opioid use, improving health outcomes, and reducing all cause and overdose mortality (Mattick, Breen et al. 2014, Nielsen, Larance et al. 2016). More recently, extended-release naltrexone (XR-NTX) has been approved by FDA for the treatment of opiate use disorder. For those who initiate treatment, the effectiveness of XR-NTX appears comparable to methadone and buprenorphine/naloxone (Morgan, Schackman et al. 2018).

Despite overwhelming evidence of efficacy and perceived potential to impact the opioid epidemic, it is estimated that less than 20% of the individuals with opioid use disorder have access to medication-assisted treatment and less than 10% actually receive treatment (CDC 2018) (Wu, Zhu et al. 2016). Several barriers have been identified and can include financial (lack of insurance coverage, inability to pay), regulatory (limited treatment capacity, waivered physicians), geographic (limited providers, treatment access), attitudinal (stigma, negative attitude towards medication assisted treatment), and logistic (lack of transportation, hours of operation) (Huhn, Tompkins et al. 2017, Sharma, Kelly et al. 2017). The strict regulatory environment and the often-long waiting list to access outpatient methadone clinic is a major barrier to treatment engagement and has helped to promote the expansion of buprenorphine/naloxone treatment that is primarily delivered in physician offices (Stancliff, Joseph et al. 2012). Increased access to buprenorphine treatment was shown to dramatically reduce the overdose rate in France (Auriacombe, Fatseas et al. 2004, Fatseas and Auriacombe 2007, Dupouy, Palmaro et al. 2017), and studies have shown a link between buprenorphine prescriptions and reduced rates of opioid overdose (Knudsen 2015, Knudsen, Havens et al. 2017).

The overall mortality in buprenorphine/naloxone treatment has been shown to no different than methadone treatment (Auriacombe, Franques et al. 2001, Kelty and Hulse 2017), and buprenorphine is safer than methadone during the 4-week period of induction (Kimber, Larney et al. 2015, Sordo, Barrio et al. 2017). Because buprenorphine is a partial agonist for mu opiate receptor and a kappa opiate receptor antagonist, the medication has a ceiling effect protecting from overdose (Fatseas and Auriacombe 2007). Increasing access to buprenorphine might raise concerns regarding diversion, however, previous studies have shown that illicit buprenorphine was not

linked with opioid overdose (Bretteville-Jensen, Lillehagen et al. 2015) and its use can enhance access to buprenorphine treatment (Cunningham, Roose et al. 2013, Fox, Chamberlain et al. 2015).

# 2.3 Interventions to increase utilization of existing MAT

Surprisingly little scientific attention has been devoted to evaluating interventions to increase the utilization of MAT. Several studies have focused on engaging individuals while they were in hospital (Sittambalam, Vij et al. 2014) or in the emergency department (D'Onofrio, O'Connor et al. 2015, D'Onofrio, Chawarski et al. 2017). These protocols have shown evidence of successful initial buprenorphine treatment engagement (21% to 74%) but without follow-up support after leaving the hospital, these rates were not sustained after 6 months. However, not all the individuals who experienced non-fatal overdose go to the hospital or, if admitted, may leave prior to the delivery of any effective intervention or referral. A recent qualitative study in out-of-treatment opiate users showed that when they got insurance coverage (mostly Medicaid), they more likely to choose the treatment available in their local community (Huhn, Tompkins et al. 2017). Community-based buprenorphine treatment intervention within harm reduction facilities (i.e. needle exchange program) was the most appealing strategy (Fox, Chamberlain et al. 2015, Fox, Sohler et al. 2017). Another approach that has been reported was based on community outreach. This project used peer-recovery specialists to engage opiate users at high-risk for overdose and link them to methadone treatment. They found that 76% initiated screening but only 54% stayed in treatment after 1 month (Scott, Grella et al. 2018). A similar strategy used a mobile unit and targeted individuals encountered at drug use venues (Daniels, Salisbury-Afshar et al. 2014) and linked the opiate users to local buprenorphine providers after helping them with insurance coverage. This program was able to link 49% of the participants to ongoing treatment but there was no measure of status at six months.

While MAT treatment capacity continues to expand, primarily through increasing numbers of buprenorphine/naloxone providers (Substance Abuse and Mental Health Service 2016), there is growing recognition of the need for more effective strategies to link opiate users to treatment. In February 2017, the Pennsylvania Department of Drug and Alcohol programs in partnership with the PA Department of Health. established a strategy for improving patient engagement in substance abuse treatment following hospital-based treatment for opioid overdose. This strategy is called the "Warm Handoff". Overdose survivors who are treated in the emergency department (ED) receive counseling and a physician's referral to be transferred directly from the ED to a drug treatment facility. The warm handoff is completed by a Peer Recovery Specialist who supports the patient and will accompany him/her to appointments for ongoing treatment following hospital discharge (Department of Drug and Alcohol Programs 2018). This strategy is being scaled up and has potential to improve the rate of completed referrals for individuals seen in the ED and needing substance abuse treatment services. No data is yet available on the efficacy of this approach.

# 2.4 MAT engagement in Philadelphia

The City of Philadelphia Behavioral Health System has established Behavioral Assessment Centers (BAC) and Crisis Response Centers (CRC) as the point of entry into MAT. In cases of emergency related to addiction-related crisis, CRCs operate 24 hours a day, 7 days per week and do emergency evaluations to help determine the most appropriate level of care and services and provide linkages to these programs. BACs provide urgent assessments for addiction services during working hours. In many cases, they will help link individuals using opioids to a community-based MAT provider as appropriate. The Philadelphia Behavioral Health System outpatient MAT capacity is 8,707 slots, as of March 13, 2018, 1,846 (21%) MAT slots were still available (21%).

# 3 The proposed study

# 3.1 Project overview

The proposed project will build upon and incorporate many of the same principles that have proven important to the success of the buprenorphine/naloxone program established by Prevention Point Philadelphia (PPP), a primary partner in this proposal. This treatment program, known as the "Stabilization, Treatment and Engagement Program" (STEP) is fully integrated within the PPP needle-exchange program that has been operational since 1991 (Bachhuber, Thompson et al. 2018). The STEP program was designed to provide treatment access to users of the syringe exchange program. Individuals identified at exchange sites throughout the City were screened at PPP's clinical offices in Kensington. Following assessment and a mandatory training, individuals would meet with the program's physician and receive an initial one-week prescription for buprenorphine/naloxone. Weekly visits and prescription refills were required for the first month. The STEP program has been able to successfully engage 124 opiate users in long-term buprenorphine maintenance treatment with a retention of 65% at 6 months and 56% at 12

#### Rapid initiation of BUP/NX Version 1: Nov-15-2018

months. More than 90% of those who remained in treatment at 12 months were opiate-abstinent (Bachhuber, Thompson et al. 2018). Importantly, and in contrast to many other programs in the City, the STEP program has a waiting list of nearly 200 individuals.

The proposed project incorporates the concept of rapid initiation of MAT and consequently, the rapid control of withdrawal symptoms. A mobile team (Nurse Practitioner, Certified Peer Recovery Specialist, and a Case manager) will provide medication, counseling and treatment engagement support for one month. During this time, individuals will be linked to community MAT providers with unused capacity.

We will determine the economic value of the mobile intervention relative to treatment as usual from the perspective of the City of Philadelphia's Department of Public Health. [name], a Health Economist in the HIV Prevention Research Division, Department of Psychiatry, Perelman School of Medicine at the University of Pennsylvania, will lead this portion of study activities with consultations with colleagues at the Center for Health Economics of Treatment Interventions for Substance Use Disorder, HCV, and HIV (CHERISH). The results of this analysis will inform future policy decisions regarding implementation of this novel, mobile strategy for rapid initiation of MAT as a method for engagement in long-term evidence-based treatment. If the intervention in this study shows positive economic value, the City of Philadelphia's Department of Public Health may scale-up the intervention to reach more people throughout the city that may be at risk of opioid overdose. Enhanced interventions may require a greater amount of resources than alternative methods of more basic interventions or the usual standard of care. However, resource-intensive interventions may be justified through the achievement of better outcomes resulting from administering enhanced procedures.

# 3.2 Innovation

Rapid induction with buprenorphine/naloxone in the community is the core innovation of the proposed research. By reducing time and geographic barriers to treatment and the control of withdrawal symptoms, the intervention will provide a one-month opportunity to link participants to an appropriate, ongoing treatment provider. This use of MAT is an innovation designed to minimize common barriers to treatment engagement. The use of buprenorphine will also allow for the transition to other MAT strategies that may be more appropriate for the individual, including methadone maintenance treatment, buprenorphine treatment, or treatment with extended-release naltrexone. The ability to engage individuals with opioid use disorder in their home environment is another important innovation of the proposed research. The mobile engagement team will include a Nurse Practitioner, a Case manager, and a Certified Peer Recovery Specialist and will begin inductions on the mobile medical unit or in the individual's home. The mobility of the team is an innovation allowing easy access to individuals who indicate interest in treating their opioid use disorder. We will assess treatment status at six months post enrollment as our primary outcome measure. With the permission of the participant, the CARES Integrated Data Systems Service Utilization database will be available to identify involvement with drug treatment and other services provided by the City prior to and following the enrollment in the study.

# 3.3 Collaborations

The proposed project will be led by investigators from the University of Pennsylvania ([name], [name], [name], and [name]) with over 60 years of collective experience in community-based substance use research in Philadelphia. These investigators have had close and longstanding collaborations with investigators from TRI and Prevention Point Philadelphia.

Prevention Point Philadelphia (https://ppponline.org): Prevention Point Philadelphia (PPP) was founded in 1991 as an underground syringe exchange organization. Over the years, PPP has evolved into a multi-service public health organization serving the most hard-to-reach populations in the toughest neighborhoods of Philadelphia. PPP was founded as a community-based SEP to address the high incidence of HIV and hepatitis C infection among people who inject heroin. Its core services now include harm reduction through syringe distribution and exchange, overdose education and naloxone distribution, provision of HIV and hepatitis C virus testing, HIV care, housing, and assistance with social services. In 2008, responding to client interest in addiction treatment and perceived lack of access by clients and program staff, PPP created a buprenorphine maintenance treatment program called the Stabilization, Treatment, and Engagement Program (STEP) that was fully integrated within the SEP. This program targets current SEP participants who express interest in cessation of heroin use. PPP will hire and support to the mobile intervention staff and maintain responsibility for the integrity of the mobile treatment and engagement service modeled after the STEP program. [name] and [name] have decades of

clinical and administrative experience in MAT delivery and will provide clinical leadership for the mobile team.

- TRI Center on Addictions at PHMC (https://www.tresearch.org): The Treatment Research Institute (TRI) was founded in 1992 as a 501(c)(3) not-for-profit organization in Pennsylvania. TRI's core mission has been to apply research to improve substance abuse policies and programs. TRI is committed to the development, evaluation, and dissemination of solutions designed to address issues related to substance use. As an independent treatment outcome evaluator, TRI has an extensive history of integrating its proven outcome assessment methods, measuring service delivery, and implementing evidence-based practices into clinical treatment programs nationally and internationally. TRI's research focuses on integrating clinical care across the various sectors affected by substance use problems, including healthcare, criminal justice. education, and community-based services. TRI is highly regarded in the substance use and mental health fields and has a reputation as a leader in translating research into practical applications. TRI is also known as the 'home' of the Addiction Severity Index (ASI), one of the most widely used assessment tools in the field. Instruments developed by TRI are among the most widely utilized by clinicians, researchers, and justice systems throughout the world. In June 2017, TRI merged with Public Health Management Corporation's R&E Group, becoming the TRI Center on Addictions at PHMC (TRI-CA). The investigators to be involved in theis project ([name], [name], and [name]) have extensive experience in treatment research with a particular focus on MAT. They will participate in the trainings and will help to manage the implementation of the research and maintain primary responsibility for the recruitment, follow-up, and assessment of individuals seeking treatment at the participating BAC/CRCs--the Treatment as Usual Group.
- Center for Health Economics of Treatment Interventions for Substance Use Disorders, HIV, and HCV (CHERISH https://cherishresearch.org): CHERISH is an NIH-funded multi-institutional research center devoted to developing and disseminating economic evidence that informs substance use treatment policy and HCV and HIV care for people who use substances. The Center serves as a national resource to increase the impact of substance use economic research. Its infrastructure is designed to enhance existing research projects, promote state-of-the art economic research methods, and improve the ability of substance use economic researchers to communicate with decision makers and address changes in today's healthcare system. CHERISH will provide the research team with training and consultation in documenting the time and resources required to deliver and monitor the intervention, as well as potential downstream cost offsets associated with effective treatment.
- Penn Injury Science Center (https://www.penninjuryscience.org): The Penn Injury Science Center is funded by a grant from the Centers for Disease Control and Prevention and brings together university, community, and government partners around injury and violence intervention programs with the greatest potential for impact. The Center promotes and perform the highest quality research, training and translation of scientific discoveries into practice and policy, in order to reduce injuries, violence and their impact to our region, the US, and locations around the world. The Center's diverse group of scientists, students, and staff are centrally co-located on the University of Pennsylvania campus in Philadelphia and represent 6 Penn Schools, 12 other Penn Institutes and Centers, 2 Level 1 Trauma Centers, and 3 Research Laboratories. The Center will provide consultation and support in geospatial analyses and mapping. Specifically, the Center will provide guidance on the initial location of the mobile treatment engagement unit.
- Philadelphia Department of Public Health (PDPH): This project has been planned and will be implemented in close cooperation with the Philadelphia Department of Public Health. We will work closely with [name], MPH and [name] who co-manage the Opioid Surveillance, Epidemiology and Prevention Program (OSEPP) at PDPH. This program focuses on collecting, analyzing, and reporting epidemiological trends in opioid abuse, including both fatal and nonfatal overdoses, use of addiction treatment services (e.g., detoxification, MAT), opioid prescribing practices, and medical consequences of drug use (HIV, hepatitis). All work is done in close collaboration with the Medical Examiner's Office (MEO), which investigates and conducts comprehensive toxicology testing on all victims of fatal overdoses. OSEPP also conducts several prevention efforts, including managing community-based naloxone distribution programs, educating providers, pharmacists, and the public about opioid overdose prevention and reversal, and training primary care providers in screening and diagnosis of opioid misuse. We will also work closely with [name] who created the city's first Opioid Misuse and Overdose Report (https://hip.phila.gov/DataReports/Opioid) by building relationships with and securing timely information from the Medical Examiner's Office, the Fire Department, the Police Department, and all major Philadelphia area emergency departments.

#### 3.4 Study Objectives

The proposed research will evaluate the ability of a mobile, rapid induction procedure to engage individuals in ongoing medication assisted treatment. Individuals meeting criteria for opioid use disorder and at high risk of opioid overdose will be enrolled in the study. Recruitment will take place in two targeted neighborhoods with a high prevalence of fatal and non-fatal opioid overdose. A total of 250 participants will be engaged in the research at the time they seek treatment. Following informed consent and determination of eligibility, 125 individuals will be enrolled as they engage with the mobile, rapid induction team and 125 individuals will be enrolled as they seek treatment from the BAC/CRC. All participants will be assessed at 1- and 6-month following enrollment. These assessments will provide data able to address each of the three aims.

- **Aim 1:** To evaluate the impact of the mobile, transitional MAT intervention on its ability to engage participants in targeted, existing MAT treatment slots at 1- and 6-month post-enrollment.
- Aim 2: To evaluate the impact of the mobile intervention on subsequent drug use and overdoses at 6-month postenrollment.
- Aim 3: To assess the acceptability and costs of the intervention. We will document the program and patient costs of delivering and participating in the intervention.

Assessments will also provide data on factors that are considered to be important determinants of retention in treatment—duration of opioid use; prior number of treatment attempts; frequency of recent use; and, depression. In addition to age, gender, and race these variables will be used in the proposed propensity analyses.

## 3.5 Rationale for Study Design

#### 3.5.1 Why no Randomization?

In the proposed project, individuals will contact our mobile team after learning about the opportunity to begin a rapid induction with buprenorphine/naloxone. As described in more detail later, awareness of the intervention will precede contact with the research team via social media, targeted advertisement, and word of mouth. This is an important feature of the research since we want to be able to measure the acceptability and demand for such a strategy. We believe that it would not be ethical to randomly assign individuals at this point to an alternative treatment option that would require additional time and referral to a different location to initiate screening and intervention. As an "open label" trial, any randomization process would also become widely known among potential participants and contaminate the perception of the mobile team as able to reliably initiate rapid treatment engagement.

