# 4.2 Total Number of Subjects

A total of 250 participants will be engaged in the research at the time they seek treatment: 125 individuals will be enrolled as they engage with the mobile, rapid induction team and 125 individuals will be enrolled as they seek treatment from the BAC/CRC (treatment as usual).

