#### 4.3 Inclusion Criteria

Participants must meet the following criteria for enrollment:

- Must be 18 years of age or older
- Opioid overdose in the prior 12 months
- Meet criteria for opioid use disorder
- Resident of Philadelphia
- Willingness and ability to participate in study procedures

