# 4.8.3 Screening assessments

For those who remain interested following discussions about the and appear to meet eligibility criteria, the consent form will be signed and the screening visit will be conducted. This visit will include completion of assessments to confirm inclusion and exclusion criteria. The Nurse Practitioner will complete a medical history, a physical exam, a rapid blood test for HIV, a pregnancy test for women, and collect 10ml of blood for liver function tests. Research staff will complete baseline assessments described in section 3.7 of this protocol. Those who are not eligible will receive a listing of treatment providers and encouraged to make contact for help with their substance use problems. For those who appear eligible following the screening visit, an appointment for initiating the intervention will be scheduled within 1 or 2 days.

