## Comparison group – Treatment as usual

During the same period of time, participants will also be recruited at the City of Philadelphia Behavioral Health System Behavioral Assessment Centers (BAC) and Crisis Response Centers (CRC) located at Episcopal Hospital serving Kensington area and Hall Mercer BAC/CRC (a University of Pennsylvania program) serving South Philadelphia area. Two research assistants from the TRI-PHMC will enroll and follow-up 125 participants at BAC/CRC. The participants will complete the same assessments at baseline, 1- and 6-month follow-up. Authorization for the Philadelphia Department of Public Health to look shared information about their subsequent use of health department services (CARES database, http://www.phila.gov/hhs/data/Pages/Cares.aspx) will also be requested in the consent form. Research staff will only conduct assessments. Treatment engagement services will be provided by the staff of the BAC/CRC as usual.

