# 5.2 Sample Size and Power Determination

Our power analysis has been based on this primary aim. Our primary hypothesis is that participants who received rapid induction will more likely be engaged in ongoing treatment at 1- and 6-month follow-up than participants who sought treatment at BAC/CRC. We will test this hypothesis at a 5% level of significance. Our principal interest is in the comparison of engagement rates between the mobile intervention and BAC/CRC groups, at months 1 and 6. Preliminary data suggest an engagement rate of about 20-30% in the BAC/CRC group. Assuming a steady loss to attrition that yields 80% completers, and a within-subject correlation of 0.3, the methods of Diggle et al. (Diggle, Heagerty et al. 2002) show that our sample size of 125 in each group yields 80% power for differences of about 15% in engagement rates between the two groups (e.g., 80% power for BAC/CRC: 25% vs. Mobile: 40%, corresponding to a RR=1.6 and an OR=2.0)

**Propensity score model to account for non-randomized allocation:** The participants are not randomly assigned to the mobile rapid induction intervention and BAC/CRC groups, so it is possible that there will be confounding of the group effect with the effects of characteristics of the participants. We will use a propensity score approach (Rosenbaum 2002, Rothman, Greenland et al. 2008) to account for this. We will use a broad range of baseline variables as covariates in a logistic regression model predicting treatment group, including age, race/ethnicity, gender, number of previous overdoses, number of previous treatments for opiate use disorder, type of opioid used, and depression. The model will yield predicted probabilities of BAC/CRC group for all participants (the propensity score), and we will create a five-level ordinal variable based on the quintiles of the propensity score. We will then include this ordinal variable as a stratum variable in our models.

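### The two arms pass different filters for wanting MAT, the outcome is enrollment in MAT, and no MAT-intent measure is described or named for adjustment

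*Combined protocol and SAP*

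**What the plan says.** **Mobile arm.** Section 3.5.1 says that "individuals will contact our mobile team after learning about the opportunity to begin a rapid induction with buprenorphine/naloxone". For those who look eligible after screening, Section 4.8.3 says that "an appointment for initiating the intervention will be scheduled within 1 or 2 days".

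**Comparison arm.** Under Sections 4.2 and 4.9.1, participants are recruited at the BAC/CRC sites at the time they seek treatment there. The study gives them no treatment: "Research staff will only conduct assessments". Section 2.4 presents these centers as the City's entry point into MAT. It also says that crisis centers carry out emergency evaluations to settle the level of care. On MAT it says: "In many cases, they will help link individuals using opioids to a community-based MAT provider as appropriate".

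**Eligibility.** Sections 4.3 and 4.4 apply to both arms. The criterion nearest to intent is "Willingness and ability to participate in study procedures". People already in MAT are excluded.

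**Outcome.** The Study Summary gives the primary endpoint as continued MAT enrollment at 6 months. The analysis for the primary aim compares engagement at months 1 and 6.

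**Adjustment.** Section 5.2 accepts that confounding is possible and relies on propensity quintiles. It describes a broad set of baseline variables that includes demographics and "number of previous overdoses, number of previous treatments for opiate use disorder, type of opioid used, and depression". Section 3.4 adds duration of opioid use and frequency of recent use. The planned sensitivity analysis concerns missing data only.

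**The concern.** In a non-randomized comparison, the variables that matter most are those that both sort people into arms and predict the outcome. Wanting to start MAT is an obvious candidate here. One arm is assembled around an advertised offer of a MAT medication. The other is assembled at sites where a person may come for MAT, detoxification, residential care or a crisis. The plan recognizes the non-medication routes itself, since the services form in Section 3.7 records detoxification and residential admissions. A comparison participant who wanted and received such care without medication would count as not engaged.

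If the arms differ on intent, part of the difference in engagement reflects who entered each arm rather than what the mobile team did. Sections 3.1 and 3.8.2 say that the results may inform City scale-up. Intent at entry also cannot be collected reliably after people have enrolled.

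**Working it through.** **1. The plan's own figure reproduces.** Inputs from Section 5.2: 25% versus 40%, 5% level (two-sided assumed, since sidedness is not stated), two time points, within-subject correlation 0.3, 80% completers, 125 per group.

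- Two-proportion sample size at one time point: 152 per arm.
- Repeated-measures factor: (1 + 0.3)/2 = 0.65, and 152 × 0.65 = 98.8 completers per arm.
- Allowing for attrition: 98.8/0.8 = 123.5, so 124 per arm against 125 planned.
- Power with 100 completers per arm: 80.5% against 80% stated.

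The sample-size arithmetic is sound. The 15-point target is the yardstick below.

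**2. Is intent captured anywhere?**

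- Eligibility (4.3, 4.4): no criterion on wanting MAT. Willingness to take part covers assessments in one arm, and assessments plus the induction program in the other.
- Consent (4.8.2): asks for interest in starting treatment in general. It is not specific to MAT and is not listed as a recorded variable.
- Baseline measures (3.7): no item described as intent, readiness or MAT preference.
- Propensity covariates (3.4, 5.2): none named. The nearest proxy is the number of previous treatments.

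**3. Size of a possible bias.** The documents give no figure for intent in either arm, so every input here is an assumption. Let m and s be the shares intending MAT in the mobile and comparison arms, and let e1 and e0 be engagement among intenders and others, the same in both arms (no intervention effect). Before any propensity adjustment:

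spurious difference = (m − s) × (e1 − e0)

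With m = 100%, the difference in points (comparison-arm rate in brackets) is:

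| s | e1/e0 = 30/15 | 35/10 | 40/5 |
|---|---|---|---|
| 80% | 3 (27%) | 5 (30%) | 7 (33%) |
| 60% | 6 (24%) | 10 (25%) | 14 (26%) |
| 50% | 7.5 (22.5%) | 12.5 (22.5%) | 17.5 (22.5%) |

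All but one of the bracketed rates lie in the 20-30% that Section 5.2 expects; the 33% cell does not.

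With m = 85%, s = 80% and a 35/10 split: (0.85 − 0.80) × 25 = 1.25 points. If s exceeds m, the sign reverses.

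**4. Effect on the test.** Take m = 100%, e1 = 40%, no true effect and 100 completers per arm. The chance of a significant result favoring the mobile arm should be 2.5%.

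- 20% of the comparison arm not intending MAT: 19% if e0 = 10%, 25% if e0 = 5%. The implied comparison rates, 34% and 33%, are above the expected range.
- 40% not intending: 60% if e0 = 10%, 75% if e0 = 5%. The implied rates, 28% and 26%, are inside the range.

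**The case against.** Several points on the other side stand.

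- A reader might infer that the comparison arm takes anyone looking for help. The documents do not support that. Both arms enroll treatment-seekers under the same criteria, and Section 2.4 calls the centers the entry point into MAT. Its sentence about linkage describes what staff do, not what patients want, and staff practice is part of usual care.
- A reader might infer that every mobile participant wants MAT. Recruitment includes street outreach (4.5), and Section 4.8.2 presents participation as a chance to consider options and expects that some will not engage. Comparison participants have already overcome time, distance and stigma barriers that the mobile team removes, which could select for stronger motivation in that arm.
- The endpoint is continued enrollment, not initiation. Because current MAT is excluded, starting is still a precondition.
- The covariate list in Section 5.2 is open-ended, and the study questionnaire is summarized rather than reproduced, so a relevant item could exist. Drug-treatment history and earlier service use in the CARES data offer partial proxies. Even so, no described measure of intent is available to add.
- The ethical argument in Section 3.5.1 is a reason not to randomize. It gives no reason to leave intent unmeasured.

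**Conclusion.** The gap is real and narrow. The arms are recruited through different filters for MAT-specific intent, that intent bears directly on the outcome, and the plan as written neither describes measuring it nor names it for adjustment. Quintiles of a propensity score cannot balance a variable left out of the model, except so far as the included covariates carry it.

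The likely direction favors the mobile arm, but it is not established, and the size is unknown. The range from about 1 to 17.5 points rests wholly on assumed shares and engagement rates. The larger values need every mobile entrant to intend MAT and half of the comparison arm not to. A reader might conclude that the planned 15-point difference would be an artifact, or that entry must be restricted to people who want MAT; the documents support neither. This is an inexpensive improvement to make before enrollment begins, not a reason to reject the design.

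**What to change.** 1. Add one graded item to the study questionnaire in Section 3.7: how soon, and how sure, the person wants to start MAT. Ask it with identical wording in both arms at screening/baseline, before any intervention or engagement service.
2. Name the item as a covariate in the Section 5.2 propensity model.
3. Report its distribution by arm and check overlap. If nearly all mobile participants give the top answer, adjustment can do little and the report should say so.
4. Add a sensitivity analysis of the primary result in participants who wanted MAT at baseline, with the cut-off on the item fixed in advance.

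Leave eligibility unchanged. The timeline in Section 3.6 has no slack: 42 × 3 = 126 enrolled per arm against a target of 125. If, say, 60% of otherwise eligible comparison participants wanted MAT, a restriction would cut enrollment to about 126 × 0.6 = 76. Keeping 125 would need 125/(42/120 × 0.6), or about 595 screened instead of 360.

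The cost is one question, one covariate and one extra analysis. The limitation is that awareness of the offer precedes contact with the mobile team, so answers there may be partly shaped by it. Adjustment will be incomplete, and the report should state this.
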